PE Audit and Feedback Pilot Study
NCT05509803
1K01HL151805
Study Protocol and Statistical Analysis Plan
October 3, 2025

Study Protocol

The objective of this study is to determine a cost-effective and scalable tool to increase schools' compliance with state PE laws. Our recent survey of all elementary school principals in REDACTED DISTRICT identified 15 elementary schools that are currently non-compliant (or unsure about compliance) with the California state PE law. We will repeat this survey to obtain current data and from the pool of schools with the lowest reported weekly PE minutes. For both the recently completed survey and for the survey to be repeated, no human subjects data are included and the principals themselves are not human subjects as no information about the principals was/will be collected. From the ~15 elementary schools identified as non-compliant with state PE law, we will stratify schools by enrollment and proportion of low-income students enrolled (two key factors known to impeded PE law compliance) and use block randomization to randomize schools to intervention (n=5) and control (n=5) arms, ensuring equal representation across strata. If schools choose not to participate, then we will re-run randomization to also include the schools not initialize randomized to participation until we have achieved our sample of 10 schools that are willing to participate.

The intervention will include use of a PE audit and feedback tool implemented by district personnel within the 5 intervention schools. The current PE Works audit and feedback tool consists of 9 binary (yes/no) PE quantity and quality indicators, including whether or not: 1) The school employs credentialed PE teachers and whether or not they teach an appropriate number of students at a time; 2) At least 200 minutes of PE and whether or not they teach an appropriate number of students at a time; 2) At least 200 minutes of PE are scheduled every 10 days, per CA education law; 3) PE class content meets instructional standards; 4) PE teachers participate in appropriate staff development and training; 5) School communicates with families about PE; 6) The school community is educated about physical activity and wellness opportunities; 7) The school's education plan includes wellness goals; 8) There is designated PE space where students can move safely; 9) The school fosters a PE culture that is inclusive of all students. This is the type of data that will be obtained/recorded by district personnel during onsite school observations and conversations with the school principal. District-level PE employees complete an onsite audit of the 9 indicators (through visual assessment and discussion with school administrators and teachers). No information about individuals will be obtained, collected, or recorded during these observations and discussions.

Once completed, data are entered into a database and a visually-pleasing 2-page report is produced for each school that: 1) describes all 9 components that were assessed; 2) highlights components where the school is succeeding; and 3) details components that need improvement, providing suggestions on how to do so. No information about individuals be entered into the database in order to generate the report. Data from the Audit and Feedback Report will be used as part of our research. We will use the 9 binary (yes/no) indicators from the report in our

analyses. We will not use data from the observations, discussions, or meetings, other than the data that goes directly into the Audit and Feedback Report. Members of the research team will not have a role in suggesting or implementing the specific changes to PE at the various schools - those decisions will be made by the district personnel and the school principal. District personnel share this report in a face-to-face meeting with the school principal. This gives the principal the opportunity to discuss and process the findings, as well as to begin creating a plan for making necessary improvements to PE, based on the feedback. All activities described above conducted by district personnel and school principals and neither the PI nor members of the study team be present for these observations, discussions, and meetings.

The PE Works tool will be updated based on formative work with New York City educators and administrators to build school-, principal-, and teacher-level capacity and creativity for, and ownership over, providing PE that meets state mandates. REDACTED DISTRICT personnel will provide technical assistance (TA) and support for school principals to develop an action plan to address PE indicators needing improvement. TA and action plan items range from helping schools create a master PE schedule that ensures appropriate time and space scheduled for all grades to meet the state PE minute mandate, to helping set up organizational systems for PE equipment to ensure proper storage and sharing across classes. The TA will be delivered by district personnel to school principals and teachers and neither the PI nor members of the study team be present for these trainings, discussions, and/or meetings.

REDACTED DISTRICT personnel will be trained to implement the PE audit and feedback tool in the fall of pilot year 1 (PY1) and will collect audit data in the spring. REDACTED DISTRICT will give feedback to school principals during one-on-one meetings in the fall of PY2. The intervention will take place over 2 years (PY2 and PY3). At the start of PY1-PY3, researchers will obtain school-level PE master schedules, which contain PE times for all classes in the school. Administrators at participating schools will either provide study team contact information to prospective 2nd and 5th grade teacher participants or will forward a recruitment email that the research team has written onto prospective participants so that prospective participants may make the first point of contact with our team if they are interested in participating. Our team will not be provided with names or contact information of prospective participants in order to recruit prospective participants. All recruitment materials and consent forms will emphasize the voluntary nature of participation in the research and that participants are free to skip/not answer any question that they do not wish to answer and are free to stop participating in the research at anytime. Once consented to participate, researchers will collect 2nd and 5th grade teachers' individual classroom PE schedules (we know PE operates differently in lower (Kindergarten – 2nd) and upper (3rd – 5th) elementary grades, which is why these two grades have been chosen.

During the fall and spring of PY1-PY3 we will collect objective data on PE class length and proportion of class spent in moderate to vigorous physical activity using the validated System for Observing Fitness Instruction Time (SOFIT) tool, observing 3 PE classes of 2 randomly selected 2nd and 5th grade teachers (n=4 teachers) and the PE teacher (if there is one) at each school on random days, per semester. Random day selection for observation days allows verification of self-reported PE minutes. SOFIT data will be collected by members of the research team who have been trained in the SOFIT protocol (and who have been CITI certified) and who have been fingerprinted and background checked and approved to visit REDACTED DISTRICT schools.

The observer will arrive 15 minutes prior to the scheduled start of the PE class to situate him/herself. During observations investigators will have no interactions with teachers or students. Once the class has arrived at the PE area (i.e. gym or blacktop), the observer will randomly select four target students to observe during the lesson (2 girls and 2 boys). No individually identifiable information will be collected on students being observed. The observer will observe Student One for 4 minutes and then rotate to focus on the four students for four minutes each until the lesson ends. A pacing MP3 played through headphones will prompt the observer to collect data every 20 seconds on 1) the activity level of the student being observed (ranging from 1 (sedentary) to 5 (very active)) and 2) what type of activity the whole class is engaged in (game play, fitness, skill acquisition, knowledge acquisition, management, or other). The observer will begin the observation period when the teacher and 51% of the class has reached the instructional station and continue until half the class has departed from the area. The observer will also collect information at the class level, including on the length (in minutes) or the PE class, weather conditions if the class took place outside, class size (and number of boys and girls in the class), and whether the teacher was administering the state FitnessGram test during class. The only identifiable information that will be collected will be the teacher name (this enables the observer to make sure he/she is observing the correct PE class), the teacher type (2nd grade, 5th grade, or PE), and the teacher's sex (M/F).

Teacher and/or student participation during the observation portion of Phase 2 requires no extra time commitment of participants outside of their normal PE class. Members of the research team will not be asking the schools/district to implement curriculum changes. Instead, we will be evaluating whether or not the tool provided feedback to the schools in a manner that allowed the schools to make the necessary changes in order to comply with state law. We will assess adoption, implementation, and maintenance of the PE audit and feedback tool through interviews with: district-level personnel involved in implementing the PE audit and feedback tool; principals in the 5 intervention schools; and all 2nd grade, 5th grade, and PE teachers observed in intervention schools. We will also conduct interviews with principals and teachers observed in the 5 control schools. These interviews will take place in PY2 and PY3 and will last approximately 20-30 minutes each. If a teacher or administrator participates in the study during both years, he/she will be interviewed twice (once in PY1 and once in PY2, after SOFIT observations are conducted in the spring). A semi-structured interview guide will enable the collection of data to assess RE-AIM components, including questions about: who teaches PE; priority for PE; the use of the PE audit and feedback tool; barriers encountered; successes and struggles with providing and sustaining mandated PE minutes; and plans for continuing to implement the PE audit and feedback tool and provide mandated minutes.

Statistical Analysis Plan

School-level demographic data will be downloaded from the California Department of Education's Data Quest website. Differences in school-level characteristics between all district elementary schools and study schools, as well as between intervention and control schools, will be determined using unpaired t-tests. Linear mixed effects models with random effects for school and grade will be used to determine 1) within-group changes and 2) difference in change between intervention and control schools in: scheduled minutes of physical education/week;

estimated minutes of physical education/week; and the proportion of observed lesson time in MVPA. All analyses will be performed using Stata/ SE (16.1).

Interview data will be coded and analyzed using a thematic analysis approach using Dedoose Qualitative Software (version 9.0.54, SocioCultural Research Consultants LLC). First, deductive coding, with codes based on predefined themes guided by the RE-AIM framework (e.g. reach, effectiveness, etc.) and Diffusion of Innovation theory (e.g. drivers of success) will be used. Second, inductive coding will be used for sub-themes that emerged from the data (e.g. specific barriers/facilitators to success and impact). Each transcript will independently coded by two researchers using an iterative process, with the researchers refining and consolidating codes and adding sub-codes and emergent codes as needed. Once the coding structure stabilizes and saturation is reached (defined as no new codes found in the data), the researchers will apply final codes to all transcripts. Once transcripts were double-coded, the researchers will review all transcripts to ensure consistent code application. If disagreements ensue, the researchers will revise and refined coding until consensus is reached. Lastly, the researchers will come to an agreement on final themes and identified drivers of successful implementation. No interviewees will provided feedback on the findings.

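### Arms appear to be drawn before schools agree and before the PY1 schedule and fall PY1 SOFIT data, although no school is treated differently until the spring PY1 audit

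*Combined protocol and SAP*

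**What the plan says.** **Selection and allocation (Study Protocol, opening paragraph).** A repeated principal survey defines the pool: "We will repeat this survey to obtain current data and from the pool of schools with the lowest reported weekly PE minutes". From about 15 non-compliant schools, "we will stratify schools by enrollment and proportion of low-income students enrolled", and the plan is to "use block randomization to randomize schools to intervention (n=5) and control (n=5) arms". Agreement comes afterwards: "If schools choose not to participate, then we will re-run randomization to also include the schools not initialize randomized to participation". This continues until ten willing schools are found.

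**Intervention (Study Protocol, description of the tool).** Only one arm receives it: "The intervention will include use of a PE audit and feedback tool implemented by district personnel within the 5 intervention schools".

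**Timeline (Study Protocol, paragraph on pilot years).** District staff "will be trained to implement the PE audit and feedback tool in the fall of pilot year 1 (PY1) and will collect audit data"; this audit is placed in spring PY1. Principals receive feedback in fall PY2, and the intervention runs in PY2 and PY3. Master schedules are obtained at the start of each pilot year. Teachers are recruited through administrators of schools already taking part. Observation starts in the first semester: "During the fall and spring of PY1-PY3 we will collect objective data on PE class length".

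**Analysis (Statistical Analysis Plan).** Mixed models estimate within-arm change and the between-arm difference in change for scheduled weekly minutes, estimated weekly minutes and the MVPA share of observed lesson time. No baseline round is named.

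The plan gives no date for the draw, does not say when schools learn their arm, and does not mention masking of schools, teachers or observers.

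**The concern.** A baseline protects a difference-in-change analysis only if the arm could not have influenced it. Here the schedule and SOFIT data that would naturally serve as baseline seem to be collected once the arm is fixed, while nothing planned for fall PY1 depends on the arm. There are three possible routes to bias:

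- **School participation.** A school may accept or decline in the light of its arm, and the re-run rule then refills the sample.
- **Teacher recruitment.** Administrators pass on the invitation. One who knows the arm could affect who volunteers. Random selection among volunteers does not undo that.
- **Measurement.** Scheduled PE time is both an audit indicator and a trial outcome, so a school expecting an audit has a reason to act early. SOFIT activity levels are coded by eye by research staff who are not described as masked.

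A school that leaves during fall PY1 would also count as a post-randomisation loss before its treatment had differed in any way.

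**Working it through.** The plan states no power, effect size, SD or ICC, so there is no figure to reproduce. The main check is the order of events.

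**1. Order of events**

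| Event | When | Differs by arm? |
|---|---|---|
| Principal survey of PE minutes | Before the draw | No |
| Draw to arms | Undated; before agreement, by the re-run rule | – |
| School accepts or declines | After the draw | Possibly |
| PY1 master schedule | Start of PY1 | Not by design |
| Teacher recruitment | In participating schools | Not by design |
| First SOFIT round | Fall PY1 | Not by design |
| Training of district staff | Fall PY1 | No |
| Onsite audit | Spring PY1 | Yes, intervention schools only |
| Second SOFIT round | Spring PY1 | Not by design |
| Feedback to principals | Fall PY2 | Yes |

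Training district staff does not require knowing which schools will be audited. The draw could therefore sit between the first SOFIT round and the audits without moving any training, audit, feedback or intervention date.

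**2. Effect on the contrast**

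Let E be the arm difference at follow-up and b the arm difference that knowledge of allocation causes at baseline. Then

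difference in change = E − b.

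If the fall and spring PY1 rounds are averaged as baseline, it is E − (b_fall + b_spring)/2. Averaging halves the fall term only if nothing carries into spring, which is the audit semester itself. Early improvement in schools expecting an audit makes b positive and shrinks the estimate. Arm-dependent refusal or volunteering could move it either way. The documents give no value for b, so no percentage follows. A master schedule already set at the start of PY1 leaves less room for reaction than SOFIT or recruitment.

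**3. Loss of one school before the audit**

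- One of five schools is 1/5 = 20% of an arm.
- With equal variance of school means, the SE ratio for 4 v 5 against 5 v 5 is sqrt[(1/4 + 1/5)/(1/5 + 1/5)] = sqrt(0.45/0.40) = 1.06.
- A simple comparison of school means would have 9 − 2 = 7 instead of 10 − 2 = 8 df. The planned mixed model need not follow that count.

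The same 4 v 5 ratio arises if a school leaves before a later draw and cannot be replaced. The 6% is therefore not a gain from moving the draw. The gain is that a departure before the draw cannot depend on the arm.

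**4. Work to finish before a later draw**

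Four classroom teachers × 3 lessons = 12 per school, or 5 × 3 = 15 where there is a PE teacher. Over 10 schools that is 120 to 150 observed lessons in fall PY1.

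**The case against.** The strongest reply is that the harm needs a fact the plan does not state: that someone who can influence participation, recruitment or measurement knows the arm in fall PY1. Schools might agree without being told their arm, and the date of the draw is itself inferred from the re-run rule and the order of the text. This stands, and it makes the point conditional. It does not remove it, because the plan describes no concealment that would rule the problem out.

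A reader might go further than the documents allow in four ways:

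- **That nothing is measured before allocation.** The repeated survey gives reported PE minutes first. What appears to follow the draw is the schedule and SOFIT data.
- **That early allocation serves no purpose.** No reason is stated, but planning five onsite audits is a plausible one.
- **That the effect is diluted by a given share.** Any such share would be assumed.
- **That change is measured from PY1.** The Statistical Analysis Plan names no baseline round.

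Two practical objections also stand. A school brought in late in fall PY1 could lack the required baseline, so replacement needs a limit. And moving the draw does nothing about losses in PY2 and PY3, the longer period at risk.

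Finally, concealing the arm until fall SOFIT is complete would deal with most of the early-reaction problem without moving the draw. That is a fair alternative where logistics require it.

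**Conclusion.** The point holds in conditional form. As written, arms are drawn before agreement, and the PY1 schedule, teacher recruitment and fall PY1 SOFIT appear to come after the draw, at least one semester before any planned difference between arms. If the arm is known to schools, administrators or observers in that semester, the difference in change can be biased through who participates, who volunteers and what is measured. Neither the size nor the overall direction can be derived from the documents.

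The conclusion rests on two readings: that the re-run rule places the draw before PY1 data collection, and that the spring audit in the timeline is spring PY1, as feedback in fall PY2 implies. The case for change rests on the low cost of a safer order, not on a demonstrated bias.

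**What to change.** **Protocol**

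1. Enrol 10 willing schools before any draw.
2. Obtain start-of-PY1 schedules and complete fall PY1 SOFIT in all 10.
3. Make one 5:5 draw, stratified as planned, after that round and before the spring PY1 audits. Delete the re-run rule.
4. Replace a school that leaves before the draw only if the replacement's start-of-PY1 schedule and fall PY1 SOFIT can still be collected. Otherwise randomise the schools that remain.

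**SAP**

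Identify fall PY1 as the pre-allocation round. Spring PY1 may still be used if it is labelled as after allocation and before feedback.

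**Cost**

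Sample size and the dates for training, audit, feedback and intervention stay as written. The district learns which five schools to audit about one semester later, and the 120 to 150 fall lessons must be observed on time or the audit window is squeezed.

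**Alternative**

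If early allocation is needed for logistics, state the reason and conceal the arm from schools, administrators and SOFIT observers until fall PY1 SOFIT is complete. This does less than moving the draw, because agreement is secured before the draw only if the enrolment step is changed as well.

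### Randomisation is re-run after refusals, with no stated agreement or concealment before arms are assigned; if schools know their arm when they decide, refusal could make the arms differ systematically

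*Combined protocol and SAP*

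**What the plan says.** The opening paragraph of the Study Protocol sets the pool: "Our recent survey of all elementary school principals in REDACTED DISTRICT identified 15 elementary schools that are currently non-compliant (or unsure about compliance". The survey is to be repeated to bring the pool up to date. From about 15 schools, the plan stratifies on enrollment and proportion of low-income students and block-randomises 5 schools to intervention and 5 to control. The next sentence deals with refusal: "If schools choose not to participate, then we will re-run randomization to also include the schools not initialize randomized to participation", and this continues "until we have achieved our sample of 10 schools that are willing to participate".

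The arms differ in the district-delivered audit, its feedback report and meeting, and "technical assistance (TA) and support for school principals to develop an action plan to address PE indicators needing improvement". Schedules, SOFIT observations and interviews apply in both arms. On timing, "REDACTED DISTRICT will give feedback to school principals during one-on-one meetings in the fall of PY2".

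The Statistical Analysis Plan compares school characteristics between all district elementary schools and study schools, "as well as between intervention and control schools, will be determined using unpaired t-tests". Mixed models then estimate the "difference in change between intervention and control schools in: scheduled minutes of physical education/week" and in two further outcomes.

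The documents do not say that schools agree to either arm before allocation, that the arm is concealed while a school decides, or that accepting schools keep their arm when randomisation is re-run. They do not ask for refusals by arm or the number of runs to be recorded.

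**The concern.** Randomisation makes arms comparable on unmeasured traits only if inclusion does not depend on the assigned arm. Here arms are named first and willingness is settled afterwards. An audit of shortcomings followed by an action plan could attract a principal or put one off. If principals know which arm they have drawn, refusal may therefore differ by arm, in either direction. If the refusing schools are also the less motivated ones, the arm with more refusals ends up with the more motivated schools.

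The between-arm difference in change is the plan's quantitative evidence on whether the tool works. Comparing change removes stable differences in level. It does not remove motivation that alters the trend. Stratifying on enrollment and low-income share does not balance motivation either. A confidence interval reflects chance imbalance, but not a systematic shift of this kind.

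**Working it through.** **1. The plan's own figure.** 5 + 5 = 10 schools, which agrees with the stated sample. The documents give no significance level, power, effect size or SD, so there is no sample-size calculation to reproduce.

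**2. Size of a possible shift.** Refusal rates and the role of motivation are assumptions, because the documents give neither. Inputs: 15 schools and 5 + 5 places (Study Protocol); motivation x with mean 0 and SD 1; logit P(refuse) = logit(p for the arm) − b·x, with b = 0.5 or 1. Here p is the refusal rate at average motivation. There were 20,000 simulated runs per setting, and strata were not modelled. The re-run rule was read in two ways: only empty places are refilled, or the whole draw is repeated without the refusing schools. Mean difference in motivation, intervention minus control, in SD (Monte Carlo SE 0.004-0.007):

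| Refusal, intervention v control | b = 1, refill | b = 1, re-run all | b = 0.5, refill | b = 0.5, re-run all |
|---|---|---|---|---|
| 25% v 5% | +0.17 | +0.11 | +0.09 | +0.06 |
| 30% v 10% | +0.16 | +0.09 | +0.09 | +0.05 |
| 40% v 10% | +0.22 | +0.12 | +0.14 | +0.09 |
| 15% v 15% | 0.00 | −0.01 | −0.01 | 0.00 |

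Swapping the rates between arms reverses the sign, with sizes within 0.02. Across all arm-dependent settings the shift is 0.09-0.22 SD (refill) or 0.05-0.13 SD (re-run all). More extreme rates give more: at 30% v 0% with b = 1, 0.28-0.29 SD (refill) and 0.17 SD (re-run all). With agreement to either arm obtained first and one randomisation, the shift is −0.01 to +0.01 in every setting of the table.

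**3. Against chance.** The SD of the chance difference between two means of 5 is √(1/5 + 1/5) = √0.40 = 0.63. Adding a shift of 0.22 gives √(0.40 + 0.22²) = 0.67, a slight overstatement because refusal also narrows the spread of motivation. Simulated directly at 40% v 10%, root-mean-square imbalance is about 0.65-0.66 for refill, re-run and agreement-first alike when b = 1. When b = 0.5 it is 0.66, 0.68 and 0.70 respectively.

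**4. Could the planned t-tests show it?** For a two-sided 5% unpaired t-test with 5 v 5, the noncentrality is d·√(5/2) on 8 df. Even with a perfect measure of motivation, power is 5.1% at d = 0.05 and 6.1% at d = 0.22 (noncentrality 0.22 × 1.58 = 0.35). Reaching 80% needs d of about 2.0.

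**5. Checks that the documents do allow.**
- The repeated principal survey yields reported weekly PE minutes, possibly for refusing schools too. The documents do not say that the first survey recorded minutes.
- "At the start of PY1-PY3, researchers will obtain school-level PE master schedules", so at most two schedule readings precede feedback.
- SOFIT observations in fall and spring of PY1 precede feedback in both arms.
- Interviews in both arms ask about the priority given to PE and about barriers. They are qualitative and, as scheduled for PY2 and PY3, follow feedback. The same paragraph also gives PY1 and PY2 for people interviewed twice, which needs reconciling.

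These are partial checks: none is a baseline measure of motivation.

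**The case against.** The wording about being randomised to participation could describe random selection of 10 schools from 15, with arms disclosed only later. No sentence says that a school learns its arm before deciding. The harm needs three things that the documents do not state: that the arm is known, that refusal differs by arm, and that refusal is tied to a trait that changes the trend. This stands, and it is why the point is conditional. It does not settle the matter, because the preceding sentence assigns arms in the same step and no consent step comes before it.

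The inferential harm is also small. If motivation were the whole outcome, a shift of 0.22 SD would raise a nominal 5% false-positive rate to about 6%. If motivation correlated 0.5 with change, the shift on the outcome would be 0.11 SD and the rate 5.3%. This stands for the assumed rates.

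Nor does agreement-first reduce total imbalance, since it may leave fewer schools. In a study titled a pilot, that is a trade of bias against variance. This stands too. What remains is that the systematic part is invisible to the planned analysis and to its confidence intervals, and that removing it takes only a change in the order of steps.

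**Conclusion.** The concern holds as a conditional weakness of minor to moderate severity. The stated rule leaves room for selection by arm, and nothing in the documents closes it. Under assumed refusal of 25-40% v 5-10%, the shift would be about 0.05-0.22 SD of motivation, in favour of the arm that refuses more. It is larger with more extreme rates and zero if refusal does not depend on arm. These figures show rough scale only and are not estimates for this trial; the documents do not anchor an effect in minutes of PE per week.

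A reader might infer that schools are told their arm and that the comparison is therefore biased, perhaps towards the intervention. The documents support neither step: they are silent on what schools know, and the direction is open. A reader might also infer that the fix makes the arms closer overall. It does not: root-mean-square imbalance is about the same, and the gain is confined to removing the systematic part.

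**What to change.** If allocation is still ahead: approach the eligible schools in random order and obtain each one's agreement to take part in either arm before any allocation is revealed. Then randomise the agreeing schools once, up to 10, balanced on enrollment and proportion low-income, with no re-runs, and analyse as randomised. If fewer than 10 agree, randomise those that do. If schools already decide without knowing their arm, a sentence saying so, and saying whether accepting schools keep their arm, largely closes the point.

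The cost is protocol wording and possibly some precision. Counting a school as agreeing only if it would accept either arm, agreement-first reaches 10 of 15 in 35-83% of runs in the arm-dependent settings, against 71-96% (refill) and 49-90% (re-run all). At 15% refusal in both arms, all three reach 10 in 95-98%. At 40% v 10%, about 8 schools are randomised on average, against 9.5 (refill) and 8.6 (re-run all). With 8 instead of 10 schools the standard error rises by √(10/8) = 1.12, about 12%. With 6, the 10th percentile in that setting, it rises by √(10/6) = 1.29, about 29%. Extending the pool beyond the roughly 15 schools would probably bring in schools that report compliance; that changes the target population and would have to be stated.

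If allocation is already done: report the number of runs, refusals by assigned arm, whether schools knew their arm when deciding, whether accepting schools kept it, and survey-reported PE minutes of refusing and accepting schools where available. Qualify the between-arm conclusion accordingly. This needs a reporting paragraph and no new data collection.
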